6. DATA COLLECTION AND PROCESSING

6.1 Measuring outcomes

Table 1 summarises what outcomes are assessed at the time points of assessments. Further details about collection of outcome data are provided elsewhere in this section.

Measure	Source	Randomisation				
		Pre*	Post			
Catheter blockage requiring intervention						
S-CAUTI requiring antibiotics						
Catheter change	D & CRF		Monthly completion for 24 months		n for	
Adverse events	CIXI		24 11011115			
NHS/Healthcare use						
			Months			
			6	12	18	24
EQ-5D-5L	PQ	✓	✓	✓	✓	✓
ICIQ-LTCqol	PQ	~	~	✓	~	✓
GSE Scale	PQ	\checkmark	✓	✓	✓	✓
ICECAP-A or O	PQ	✓	✓	✓	✓	1
Satisfaction with treatment	PQ	~	~	✓	✓	✓
Participant/ relative, friend or informal carer's time and travel	PQ				~	

CRF = Case Report Form, D = LTC Diary/Calendar; PQ = participant/ relative, friend or informal carer completed questionnaire. *Pre randomisation is after informed consent has been given but prior to randomisation

6.2 Baseline data (data collected prior to random allocation to treatment)

Participants with or without the assistance of their relative, friend or informal carer complete the baseline questionnaire prior to randomisation. The baseline questionnaire includes the EQ-5D-5L, the ICIQ-LTCqoI, GSE Scale and the ICECAP-A or ICECAP-O. A catheter urine sample for pH testing will obtained from all participants and tested immediately using the simple urine dipstick test.

The local research team completes the baseline CRF which includes the following information: gender; age, residential status, neuropathic bladder; previous blockages requiring intervention in last 6 months; previous S-CAUTI requiring antibiotics in last 6 months and other catheter-related history.

6.3 Follow-up

Participants (or the relative, friend or informal carer carrying out the washout) record LTC related events on their LTC calendar/diary including: LTC blockage requiring intervention (as defined in section 5.1); LTC change and the reason; adverse events such as S-CAUTI; antibiotics use for S-CAUTI; emergency catheter washout and its indication; treatments in primary or secondary care. The CATHETER II LTC diary is adapted from a purpose built diary that has been successfully used in an RCT in this field (permission already obtained from Wilde et al 2017¹)

The primary outcome, a number of the secondary outcomes, adverse events, and adherence are collected approximately monthly for 24 months from the participant and/or the relative, friend or informal carer carrying out the washout. A member of the research team, as delegated, completes the CRF over the phone or by agreed methods e.g. post/ email. A face to face interview will be arranged by the research team if/ when appropriate e.g. significant missing data from the monthly

contact. Where local site teams capture follow up information directly to the CATHETER II electronic CRF, the electronic record is the source data.

The EQ-5D-5L, the ICIQ-LTCqol, GSE Scale and the ICECAP-A/ or ICECAP-O and satisfaction with treatment are completed by participants with or without assistance from their relative, friend or informal carer at 6, 12, 18, and 24 months after randomisation.

Participants and their relative, friend or informal carer, if applicable, are asked to complete a time and travel questionnaire at 18 months after randomisation. This is to be used to estimate costs to participants.

We offer and use all methods of delivery and collection of questionnaires and reminders including use of research teams, telephone, post, e-mail (e-mail verification is used to validate e-mail addresses), and web based taking into account each participant and/or their relative, friend or informal carer(if applicable) stated preferred means of receiving and completing the measures (recorded on the contact preference form). One reminder for the questionnaire is sent to participants and their relative, friend or informal carer, if applicable, by post, email, or phone taking into account any preferences they may have for mode of communication.

A small token of appreciation (shopping voucher(s)) is sent to participants on receiving their completed follow up questionnaires, unless they opt out on the study consent form.

If a participant stops using a long-term catheter (no catheter in use) >=28 days, all data collected up to the point of stopping long term catheter use are retained and used in the analysis. We will ask these participants with or without the assistance of their relative, friend or informal carer, if applicable, to complete one further (exit) EQ-5D-5L with one reminder.

6.4 Future research, including long term follow-up

We plan to seek funding and the necessary approvals for future research or to follow up CATHETER II participants. We will ask for their permission to be contacted about such studies. The PIL informs the participants of this (and that we would hold their details for 10 years after the end of the study to facilitate this).

6.5 Change of Status/Withdrawal procedures

Participants are free to withdraw their consent to participate at any time.

Participants are followed up for the trial outcomes wherever possible. If a participant does not receive or continue with their allocated intervention, either because of participant preference or change of circumstance, they continue to participate as per trial data collection schedule unless the participant declines to participate in the data collection schedule.

All data collected up to the point of complete withdrawal are retained and used in the analysis. Participants who do not complete their trial follow up but for whom any outcome data are available are included in the study analysis.

If a participant stops using a long-term catheter (no catheter in use >=28 days), all data collected up to the point of stopping long term catheter use are retained and used in the analysis. We will ask these participants with or without the assistance of their relative, friend or informal carer, if applicable, to complete one further (exit) EQ-5D-5L with one reminder.

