5.2 Secondary outcome measures

Secondary outcomes include:

- S-CAUTI requiring antibiotics use (as defined by Pickard et al¹⁶)
- Duration of LTC in use, catheter change due to other reasons than blockage
- Adverse events
- Hospital admissions, GP/ nurse outpatient visits for catheter related complications
- Generic quality of life as assessed by EQ-5D-5L¹⁷ (EuroQol questionnaire 5 dimensions 5 levels)
- Condition specific quality of life assessed by ICIQ-LTCqol¹⁸ (International Consultation on Incontinence Modular Questionnaire – Long Term Catheter quality of life)
- Adherence to allocated interventions
- Patients' convenience and satisfaction assessed by an adapted version of the abbreviated Treatment Satisfaction Questionnaire for medication¹⁹
- Impact on day to day activities using The General Self-Efficacy Scale (GSE)²⁰ and ICECAP-A (ICEpop CAPability measure for Adults) (≤ 65 years) or ICECAP-O²¹ (ICEpop CAPability measure for Older people) > 65 years
- Time and travel costs for patients and their relatives, friends or informal carers
- Discontinuation of catheter use
- Events changing type and/or frequency (or cessation) of catheter washouts in arms B and C and rates of commencing on prophylactic washouts in arm A.

Qualitative study outcomes:

- Participants' experience of LTC-related AEs such as blockage, S-CAUTI, urinary incontinence, bladder pain
- Participants' attitudes/ preferences to washout versus no washout policies and expected outcomes (prior to randomisation or knowing their allocated study group) (acceptability);
- Participants' experience with washout/ no washout policies and evaluation of outcomes (satisfaction)
- Clinicians attitudes towards influence of washout policies on outcomes
- Participants' and clinicians' experience of training provided and enactment of the treatment skill. This would clarify the fidelity of the intervention.

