10.2 Health benefit measurement

Effectiveness in economic evaluation is measured in terms of quality adjusted life years (QALYs) gained for each washout policy compared to standard LTC care. QALYs are derived using response data from EQ-5D-5L administered at baseline, 6, 12, 18 and 24 months as part of the study questionnaires. EQ-5D response data are to be converted into health state utilities using UK population tariffs.²⁷ QALYs are calculated using an area under the curve approach, applying linear interpolation between the health state utility scores at baseline and the follow-up time points. Participants who die within the study follow-up period are to be assigned a zero utility weight from time of death.

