10.3 Analysis of trial data

Multiple imputation methods are to be used to handle missing cost and utility data. The incremental cost-effectiveness ratio (ICER), calculated as the ratio of the difference in mean costs and QALYs between the alternative strategies, is to be estimated using generalized linear models with adjustment for minimisation variables and, where appropriate, baseline measures. Uncertainty surrounding the joint differences in mean costs and effects are to be characterised using non-parametric bootstrapping, and presented graphically on the cost-effectiveness plane and using cost effectiveness acceptability curves (CEAC). Sensitivity analysis is to be used to explore the impact of deterministic assumptions on the results of the economic analysis.

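### Scheduled data collection appears to stop once a participant has been catheter-free for 28 days, although the primary economic outcome needs utility and resource-use data to 24 months

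*Protocol*

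**What the plan says.** Sections 6.3 and 6.5 of the Protocol give the same rule for a participant who has had no catheter for 28 days or more: "all data collected up to the point of stopping long term catheter use are retained and used in the analysis". The only later collection they name is a request "to complete one further (exit) EQ-5D-5L with one reminder". No resource-use form is mentioned and no date is set for the exit form.

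Section 6.5 treats a different event differently. Of participants who do not receive or continue their allocated intervention it says that "they continue to participate as per trial data collection schedule unless the participant declines to participate in the data collection schedule". It also has a general line: "Participants are followed up for the trial outcomes wherever possible".

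On the economic side:
- Section 5.1 makes cost per QALY gained the primary economic outcome.
- Section 10.2 states that "QALYs are derived using response data from EQ-5D-5L administered at baseline, 6, 12, 18 and 24 months". It gives a utility rule for time after death, but none for time after catheter use ends.
- Section 10.1 counts resource use over the whole 24 months, and Table 1 in section 6.1 schedules healthcare use monthly for that period.
- Section 10.3 states: "Multiple imputation methods are to be used to handle missing cost and utility data".

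Section 5.2 lists "Discontinuation of catheter use" as a secondary outcome.

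**The concern.** The exit rule is built around the primary clinical outcome. With catheter days as the offset (section 9), a person without a catheter adds no exposure, and nothing is lost by ceasing to record blockages while none can occur. The primary economic outcome has a different clock: 24 calendar months from randomisation, whatever the catheter status.

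The trigger occurs after randomisation and is itself one of the trial's outcomes. If it is more frequent in one arm, that arm loses more QALY and cost data. Those who come off a catheter may also differ in utility and healthcare use from those who remain on one, so the data may not be missing at random. This is a rule about what is collected, and no later analysis document can recover data that were never gathered. The questionnaire outcomes collected every six months are affected in the same way.

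**Working it through.** **1. Does collection end?** The protocol does not say so outright. Three features point that way: the form is called an exit form and is the one further form, the data used are those up to stopping, and section 6.5 gives the full schedule to those who stop the intervention but not to those who stop the catheter. The general wherever-possible line does not displace the specific rule. At the least, the two need reconciling.

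**2. The plan's own figures.** The protocol gives no discontinuation rate, so there is no figure on this point to reproduce. Its one design figure, 200 per arm, concerns the blockage rate. With rates 0.0118 and 0.0089 per day, 680 days and dispersion 0.6 (section 8.1), the variance term is (1/680)(1/0.0118 + 1/0.0089) + 2 × 0.6 = 1.490. At 90% power this gives 197 per arm if the 2.5% level is one-sided (232 if two-sided). Nothing below changes it.

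**3. What one participant loses.** Assume the exit form arrives about one month after a stop at month s. Unobserved share = (24 − (s + 1)) / 24.

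| Stop at month | Unobserved share | Scheduled EQ-5D-5L points lost |
|---|---|---|
| 3 | 20/24 = 83% | 4 |
| 6 | 17/24 = 71% | 3 |
| 9 | 14/24 = 58% | 3 |
| 12 | 11/24 = 46% | 2 |
| 18 | 5/24 = 21% | 1 |

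No resource use is collected for the unobserved part. Deaths are recorded as SAEs (section 7.2), but SAEs only until the last trial follow-up (section 7.3.1). A death after exit might therefore be missed, and the zero-utility rule of section 10.2 could not then be applied.

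**4. What an arm loses.** Assume 5–20% discontinue and lose 25–75% of the window:
- low: 0.05 × 0.25 = 1.3% of the arm's person-time
- high: 0.20 × 0.75 = 15%

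**5. Shift in the QALY difference.** Shift = (difference between arms in proportion discontinuing) × (utility error in unobserved time) × (years unobserved). Assume a difference of 2–10 percentage points, an error of 0.05–0.10 that is the same in both arms, and one year unobserved on average:
- low: 0.02 × 0.05 × 1 = 0.001
- middle: 0.05 × 0.10 × 1 = 0.005
- high: 0.10 × 0.10 × 1 = 0.010

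At an assumed £20,000 per QALY, these are worth £20, £100 and £200 per participant.

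If unobserved time were simply not counted, with an assumed utility of 0.6, the shift would be 0.02 × 0.6 = 0.012 to 0.10 × 0.6 = 0.060. The protocol does not plan this, since section 10.3 imputes missing data. It also does not say whether time after stopping counts as missing.

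**The case against.** The strongest reply is that the protocol states a retention rule and nowhere says that collection ceases. That is correct as to the words, and the truncation is an inference. But the exit form and the contrast with the rule for stopping the intervention leave little room for another reading.

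Second, the imputation model is not given and properly belongs in an analysis plan. Arm, discontinuation and the exit score could all enter it. This stands against any claim that imputation will use the wrong people. It does not remove the difficulty that, after stopping, any model has one utility score and no costs to learn from.

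Third, much catheter-related resource use should fall away once the catheter is out, so part of the later cost is absent for structural reasons. This also stands, but replacement-care costs may remain and would not be seen.

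Fourth, numbers may be small: entry requires no plan to discontinue (section 4.2), and section 1.1 cites a mean duration of use of 6 years. This bears on size and is accepted.

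A reader might go further and infer that the missing data are caused by treatment, that they are not missing at random, or that the economic comparison is no longer by intention to treat. The documents support none of these. Nothing in them shows that washouts alter the need for a catheter. A difference between arms would not by itself make the data not missing at random. Everyone with any outcome data stays in the analysis (section 6.5).

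**Conclusion.** The point holds as a mismatch between the collection rule and the primary economic outcome. On the natural reading of sections 6.3 and 6.5, a participant who stops using a catheter contributes one more utility score and no further resource use, while the QALY and cost analysis covers 24 months. The imputation assumption needed to bridge this can hardly be checked within the trial.

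The likely effect is small: about 0.001 to 0.010 on the QALY difference, direction unknown. It rests entirely on assumed discontinuation, timing and utility error, because the protocol supplies none of these.

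Two further inferences should be resisted. The blockage rate over observed catheter days is not biased by catheter-free time, because that time is outside the offset. Nor does the protocol say that blockages after a catheter is re-inserted are lost. It is silent on re-insertion, and that silence should be filled.

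The change is worth making because it is cheap and the data cannot be reliably recovered later.

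**What to change.** In sections 6.3 and 6.5, state that participants who stop catheter use continue the scheduled EQ-5D-5L, healthcare-use and death recording to 24 months unless they decline, as section 6.5 already provides for those who stop the intervention. The exit EQ-5D-5L can be kept for those who decline the rest. State also that blockage and catheter-day recording resumes if a catheter is re-inserted. Keep catheter days as the offset in the primary clinical analysis.

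If continued collection is not feasible, the minimum is to define how time after stopping enters the QALY and cost totals, including how an exit score taken between scheduled visits is used. This is weaker, because it states the assumption without supplying data to test it.

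The cost is an amendment and, for a minority of participants, a few more questionnaires and contacts that are already on the schedule. The sample size does not change.

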6.6 Data processing

Local study team members as listed on the delegation log can enter locally collected data. Staff in the Trial Office work closely with local study team to ensure the data is as complete and accurate as possible.

7. SAFETY

ISRCTNxxxxx IRAS 259559

7.1 Standard definitions

An **adverse event** (AE) is any untoward medical event affecting a clinical trial participant. Each initial AE is considered for severity, causality or expectedness and may be reclassified as a serious adverse event based on prevailing circumstances.

A serious adverse event (SAE), is any AE, that:

- results in death;
- is life threatening (i.e. the subject was at risk of death at the time of the event; it does not refer to an event which hypothetically might have caused death if it were more severe);
- requires hospitalisation or prolongation of existing hospitalisation*;
- results in persistent or significant disability or incapacity;
- is otherwise considered medically significant by the investigator.

*Hospitalisation is defined as an overnight hospital admission.

7.2 Trial specific considerations

In this trial, the following events are expected and are reported as SAEs:

- Bacteraemia/ urosepsis
- Pyelonephritis
- Allergic reactions
- Erosion (tearing) of the urethra, primarily the urinary meatus
- Creation of a false passage/ urethral fistula
- Autonomic dysreflexia
- Damage to rectum/ peritonitis
- Urethritis
- Epididymitis.

In this trial, the following events are anticipated and are captured as primary or secondary outcomes rather than being captured through adverse event or serious adverse event reporting processes.

- Catheter blockage
- S-CAUTI
- Urinary retention
- Catheter change due to other reasons such as S-CAUTI, Urinary Leakage
- Catheter twists/ kinking/ dislodgement
- Bladder pain/ spasm
- Haematuria/ pyuria
- Urethral trauma/ bleeding
- Urinary bypass/ urinary leakage/ urinary incontinence
- Bladder stones
- Urethral stricture/ narrowing
- Irritation.

Hospitalisations or prolongations of an existing hospitalisation due to any of the LTC related events listed within the primary or secondary outcomes will not be considered or recorded or reported as an SAE. They are recorded as outcomes and regularly reviewed/ monitored by the DMC.

Hospitalisations for treatment planned prior to randomisation and hospitalisation for elective treatment of a pre-existing condition will not be considered or recorded or reported as an SAE. Complications occurring during such hospitalisation will also not be considered, recorded or reported as an SAE.

In this trial, all other SAEs that are related to the catheter and associated washout procedures are recorded. In addition, all deaths (any cause) are also recorded as SAEs. Events that are serious but are not related to the catheter or associated washouts will not be recorded as SAEs.

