Current practice for the prevention and/ or management of LTC blockage is predominately twofold: more frequent change of the catheter and/or the use of washout solutions (saline or acidic) to irrigate/ flush the catheter. The former imposes substantial workload on nursing staff and can be associated with higher risk of S-CAUTI, while the Cochrane review concluded that there is insufficient evidence to determine if prophylactic washout policies were beneficial or harmful².

- S-CAUTI secondary to bacteriuria or candiduria is another common problem in LTC users (57%)¹. There are a number of definitions for S-CAUTI: the British Infection Association definition relies on clinical diagnosis only while the Centre for Disease Control and Prevention (CDC) definition incorporates systemic and localising clinical findings with laboratory-based criteria.¹² Pickard et al¹³ in the CATHETER study defined S-CAUTI based on the development of symptoms and signs of UTI and prescription of antibiotics by the responsible clinician. This

is a modification of the CDC definition that is more pragmatic and relevant to patients and practice in the UK. In CATHETER II we opted to use the latter definition for SCAUTI.

Muncie et al¹⁴ compared saline washouts versus no washouts policy over 24 weeks in a limited population and showed no significant differences in S-CAUTI/ 100 days of catheter-use. Concerns exist that use of washouts can damage the bladder mucosa and possibly increase risk of S-CAUTI. NICE CG139 recommend that "Catheter washouts must not be used to prevent catheter associated infections"³

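### Section 7.2 sets no precedence between its list of reportable SAEs and its exemption for outcome events, so an admission for urosepsis or pyelonephritis can fall under opposite rules

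*Protocol*

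**What the plan says.** Section 7.2 of the protocol contains three rules that bear on this point.

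- A first list of events is introduced with the statement that "the following events are expected and are reported as SAEs". It includes "Bacteraemia/ urosepsis", "Pyelonephritis" and "Erosion (tearing) of the urethra, primarily the urinary meatus".
- A second list of anticipated events is to be "captured as primary or secondary outcomes rather than being captured through adverse event or serious adverse event reporting processes". It includes S-CAUTI and "Urethral trauma/ bleeding".
- SAE status is ruled out for some hospitalisations and prolongations of them: those "due to any of the LTC related events listed within the primary or secondary outcomes will not be considered or recorded or reported". The next sentence adds that they are recorded as outcomes and monitored by the DMC.

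Section 1.1 explains what S-CAUTI means in this trial. It cites an earlier catheter trial that "defined S-CAUTI based on the development of symptoms and signs of UTI and prescription of antibiotics by the responsible clinician", and adopts that definition. Section 5.2 lists S-CAUTI requiring antibiotics as a secondary outcome. It also lists adverse events in general and hospital admissions for catheter-related complications.

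**The concern.** The two lists use different words but do not describe separate sets of events. Urosepsis and pyelonephritis in a catheter user, once treated with antibiotics, can also satisfy the trial's description of S-CAUTI. If such a participant is admitted overnight, one sentence of 7.2 requires an SAE report and another forbids it. A site following either sentence can say that it complied with the protocol.

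The label decides what happens next. An SAE leads to review of hospital notes and laboratory reports (7.3.2), evaluation of seriousness, causality and expectedness by a medically qualified person (7.3.3), and inclusion in the SAE summaries sent to the ethics committee, funder, TSC and DMC (7.3.5). An outcome event is recorded from diaries and roughly monthly contacts (6.3), and the protocol requires no causality assessment for it.

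Safety is part of the research question (section 2), and section 1.1 raises the possibility that washouts increase the risk of S-CAUTI. The trial is open (section 3) and planned for about 70 sites (4.1), so staff who know the allocation would choose between the labels without a rule.

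**Working it through.** No arithmetic applies; the point depends on no rate, power or sample size. The check sets the rules side by side and asks whether one event can meet both.

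| Event | Rule requiring SAE reporting | Rule against SAE reporting |
|---|---|---|
| Overnight admission with urosepsis, antibiotics prescribed | "Bacteraemia/ urosepsis" is on the first list | Can meet the S-CAUTI description in 1.1; S-CAUTI is on the second list and in 5.2, so the admission bar applies |
| Overnight admission with pyelonephritis, antibiotics prescribed | "Pyelonephritis" is on the first list | As above |
| Admission with a urethral tear and bleeding | "Erosion (tearing) of the urethra, primarily the urinary meatus" is on the first list | "Urethral trauma/ bleeding" is on the second list; the admission bar applies only by inference |

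**Step 1: does the S-CAUTI description exclude the severe infections?** As stated in 1.1 it has two elements: symptoms and signs of urinary infection, and an antibiotic prescription. It sets no upper limit of severity and does not carve out upper-tract or systemic infection. On the protocol's own wording, overlap is possible.

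**Step 2: does the admission bar make an exception for first-list events?** It does not. It covers events listed within the primary or secondary outcomes. Because 5.2 names adverse events and catheter-related admissions among those outcomes, a literal reader could apply the bar to a first-list admission without calling it S-CAUTI at all.

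**Step 3: is there a tie-break elsewhere?** The residual clause in 7.2 records all other catheter- or washout-related SAEs, but it does not rank the two lists. Section 7.3.1 refers back to the criteria in 7.2. Sections 7.3.2 to 7.3.5 describe what is done with an SAE once it qualifies, not which rule decides. No precedence statement was found.

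**Step 4: how strong is the urethral case?** Weaker. Section 5.2 does not name urethral trauma, so its status as an outcome rests on the second list and on the general adverse-events entry. The overlap rests on the ordinary meaning of trauma, and the protocol lists tearing separately.

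**Step 5: what safeguards remain under either reading?** Barred admissions are recorded as outcomes and monitored by the DMC (7.2). Adverse events captured as secondary outcomes, S-CAUTI in particular, are summarised to the DMC regularly, or earlier if indicated (7.3.5). Deaths from any cause are SAEs (7.2). First-list events are declared expected. The 24-hour sponsor notification (7.3.4) and the 15-day ethics report (7.3.5) both require an unexpected event, so neither would normally be triggered by either classification.

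**The case against.** The best defence is that the specific term overrides the general one. Urosepsis, pyelonephritis and tearing are named on the first list and nowhere on the second, so an admission diagnosed as urosepsis is naturally an SAE and an uncomplicated S-CAUTI is an outcome. That is a sensible reading and probably what was intended. The text does not state it, however, and the admission bar is worded without exception.

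It can also be said that section 1.1 only paraphrases the S-CAUTI definition, and that 5.2 defers to a cited source. This stands as a limit. A reader might infer that all treated urosepsis and pyelonephritis fall under both rules. The documents show that they can, not that they always do.

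The safeguards are real, and they rule out any claim that serious infections would go unseen. The S-CAUTI comparison itself does not depend on SAE labelling, because S-CAUTI is collected monthly in all arms. Differential labelling by arm is a possibility in an open trial; nothing in the protocol shows that it will occur.

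A reader might go further and infer that the second-list exemption should be narrowed, because 7.1 makes a life-threatening event serious while the second list exempts its events whatever their severity. The documents do not support treating that as an error. Exempting anticipated outcome events is a deliberate, trial-specific choice with DMC review attached, and its breadth is a trade-off for the sponsor.

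**Conclusion.** The point holds as a conflict between stated rules in 7.2. An admission for antibiotic-treated urosepsis or pyelonephritis can be both required and forbidden as an SAE, with no precedence given. The same may be true, less clearly, of a urethral tear with bleeding. The conclusion assumes that the S-CAUTI description in 1.1 is the one sites will apply.

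The consequence is inconsistent SAE classification between sites, possibly between arms, and loss of the notes review and causality assessment for events handled as outcomes only. It is not loss of oversight. A reader might want a number of affected participants, but the protocol gives no rate at which S-CAUTI progresses to urosepsis, pyelonephritis or admission. Any count would rest entirely on an assumed rate, so none is offered. The sponsor should correct this: it concerns safety reporting in a trial whose question includes safety, the harm is partly mitigated, and the correction is small.

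**What to change.** Reconcile the passages in 7.2 with a short precedence statement that makes four things explicit:

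1. An event on the first list is recorded as an SAE even when it leads to admission or also counts as S-CAUTI or urethral trauma.
2. The second-list exemption and the admission exemption do not apply to first-list events.
3. Such an event is counted both as an outcome and as an SAE.
4. The rule is applied identically in all three arms.

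The exemption for other second-list events can stay as it is. The change affects reporting only, not treatment.

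The cost is a sentence or two in 7.2 with matching wording in the SAE guidance, the amendment steps in 14.1, and probably a modest number of extra SAE forms. Some events will appear in both the outcome and SAE tables, which a footnote can explain.
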